10.3 Efficacy Analysis

10.3.1 Analysis of Primary Efficacy Endpoint

Not applicable.

10.3.2 Analysis of Secondary Efficacy Endpoints

The analysis of Secondary efficacy endpoints will be conducted for Treatment Cohort Period 1 only.

10.3.2.1 Definition of Secondary Efficacy Endpoints

10.3.2.1.1 Definition of Secondary Efficacy Endpoints

Absolute change from baseline in $LCI_{2.5}$

$LCI_{2.5}$ represents the number of lung turnovers required to reduce the end tidal inert gas concentration to 1/40th of its starting value.

The LCI assessments are derived from N_2 -multiple-breath washout (MBW) testing. Each MBW will be performed in multiple replicates at each visit and the final LCI value will be calculated from all the technically acceptable washout replicates, as determined by a central reader. The final LCI value at each visit will be the value calculated based on the multiple replicates per the algorithm provided by the LCI central reader as detailed in Appendix C.

Absolute change from baseline in sweat chloride

For each subject and at each time point, 2 sweat chloride measurements will be collected: 1 from the right arm, and 1 from left arm. Of the 2 measurements, only the sweat chloride value obtained from a sample volume $\geq 15 \mu\text{L}$ will be included in any analysis (i.e., values from samples with volumes $< 15 \mu\text{L}$ will be considered missing for analysis purposes). If a subject has replicated measurements at a post-baseline time point, then the median of the values will be used in data analyses. The sweat chloride results for the left and right arms will be averaged and used in the analysis if the sweat chloride values for the left and right arms are both $\geq 15 \mu\text{L}$; if only 1 arm is $\geq 15 \mu\text{L}$, then only that value will be used.

Note: Any sweat chloride values reported as $< 10 \text{ mmol/L}$ or $> 160 \text{ mmol/L}$ will be considered missing for analysis purposes.

Absolute change from baseline in BMI

BMI will be calculated as the following:

$$\text{BMI} = \text{Weight (kg)} / (\text{height (m)}^2)$$

Absolute change from baseline in CFQ-R respiratory domain

The CFQ-R^{3,4,5} is a validated CF-specific instrument that measures quality-of-life domains. There are two different versions of CFQ-R forms in this study:

- CFQ-R Child Version has a total of 35 questions to form 8 domains. All questions are scored 1, 2, 3, or 4.
 - Interviewer Format for Children Ages 6 to 11
 - Self-completion for Children ≥ 12 years of age after the Day 1 Visit of Study 110
- CFQ-R for Parents/Caregivers (subjects 13 years and younger) has a total of 44 questions to form 11 domains. Question 37 is scored 1, 2, 3, 4, or 5 and is not used in calculating any domains; all the other 43 questions are scored 1, 2, 3, or 4.

Note that subjects will complete the same version of the CFQ-R that was completed in the previous studies (Study 109 or Study 011B), regardless of whether the subject subsequently turns 14 years of age during the study.

For both CFQ-R versions, to calculate the score for each domain, the response scores on the negatively phrased questions are reversed (reversed scores = 5 – response scores). Therefore, 1 always represents the worst condition and 4 always represent the best condition. In each domain, in cases where individual questions were skipped, the missing scores are imputed with the mean score of the non-missing questions for that domain rounded to the nearest integer.

The scaled score for each domain ranges from 0 (worst condition) to 100 (best condition) and is calculated as follows:

$$\text{Scaled score for a domain} = 100 \times (\text{mean (scores of all questions in that domain)} - 1)/3$$

The scaled score for a specific domain will not be calculated if more than half of the questions in the domain have missing scores.

Table 10-5 and Table 10-6 provide the questions included in each domain, the questions with the reversed scores, as well as the maximum number of missing questions for the CFQ-R Child version and the CFQ-R Parents/Caregivers Version respectively.

Table 10-5 CFQ-R Child Version (Interview Format for Children Ages 6 to 11, and Self-completion for Children ≥ 12)

Domain	Questions		Reversed questions	Maximum number of missing questions
	Total	Individual		
Physical	6	1, 2, 3, 4, 5, 6	1, 2, 3, 4, 5	3
Emotion	8	7, 8, 9, 10, 11, 12, 13, 14	14	4
Social	7	20, 21, 22, 23, 24, 25, 26	20, 22, 24, 26	3
Body	3	27, 28, 29	-	1
Eat	3	15, 17, 19	19	1
Treatment burden	3	16, 18, 30	18	1
Respiration	4	31, 32, 33, 34	-	2
Digestion	1	35	-	0

Table 10-6 CFQ-R for Parents/Caregivers (Subjects 13 Years and Younger)

Domain	Questions		Reversed questions	Maximum number of missing questions
	Total	Individual		
Physical	9	1, 2, 3, 4, 5, 13, 14, 15, 16	15	4
Vitality	5	8, 9, 10, 11, 12	10, 12	2
Emotion	5	6, 7, 23, 25, 26	6	2
School	3	27, 28, 29	28	1
Body	3	19, 20, 21	-	1
Eat	2	17, 44	-	0
Treatment burden	3	18, 30, 31	31	1

Table 10-6 CFQ-R for Parents/Caregivers (Subjects 13 Years and Younger)

Domain	Questions		Reversed questions	Maximum number of missing questions
	Total	Individual		
Health perceptions	3	22, 24, 32	22, 24, 32	1
Weight	1	33	-	0
Respiration*	6	34, 35, 36, 38, 39, 40	37	3
Digestion	3	41, 42, 43	-	1

*: Question 37 not used to calculate a domain.

10.3.2.1.2 Definition of Other Secondary Efficacy Endpoints

Absolute change from baseline in LCI_{5.0}

LCI_{5.0} represents the number of lung turnovers required to reduce the end tidal inert gas concentration to 1/20th of its starting value.

As clarified with regard to LCI_{2.5}, each MBW will be performed in multiple replicates for each visit and the final LCI value will be calculated from the technically acceptable washout replicates by a central reader. The final LCI value at each visit will be the value provided by the LCI vendor based on the triplicates.

Absolute and relative change from baseline in ppFEV₁

ppFEV₁ is the ratio of FEV₁ (L) to the predicted FEV₁ (L), expressed as a percentage. The predicted FEV₁ will be calculated using the Wang¹ standards with details in Appendix F.

Relative change in ppFEV₁ is the ratio of absolute change in ppFEV₁ to baseline ppFEV₁.

Absolute change from baseline in BMI-for-age z-score

BMI, adjusted for age and sex, will be referred to as BMI-for-age z-score (BMI z-score). BMI z-score will be calculated by using Centers for Disease Control and Prevention (CDC) growth charts⁶. The BMI z-score will be calculated as follows:

$$z = \begin{cases} \frac{\left(\frac{X}{M}\right)^L - 1}{LS}, & L \neq 0 \\ \frac{\ln\left(\frac{X}{M}\right)}{S}, & L = 0 \end{cases}$$

Where X is the derived BMI value in kg/m² based on the raw weight and raw height and L , M , and S are selected from the CDC BMI-for-age chart by subject sex and age. The BMIAGE file contains these parameters by sex (1=male, 2=female) and age; it is available at: http://www.cdc.gov/growthcharts/percentile_data_files.htm. Additionally, SAS code for calculating percentiles and z-scores is available at: http://www.cdc.gov/growthcharts/computer_programs.htm.

NOTE: The CDC BMI-for-age charts are designed for use in pediatric populations (2 to 20 years of age).

Absolute change from baseline in weight and weight-for-age z-score

Weight, adjusted for age and sex, will be referred to as weight-for-age z-score (weight z-score). The calculation of weight z-score is similar to that of BMI z-score (using the CDC growth charts and the derivation described above). Using the same equation above, X in the equation is the collected weight and L , M , and S parameters are selected from the CDC weight-for-age chart. The WTAGE file contains these parameters by sex and age; it is available at the website http://www.cdc.gov/growthcharts/percentile_data_files.htm.

NOTE: The CDC growth charts are designed for use in pediatric populations (2 to 20 years of age).

Absolute change from baseline in height and height-for-age z-score

Height, adjusted for age and sex, will be referred to as height-for-age z-score (height z-score). The calculation of height z-score is similar to that of BMI z-score (using the CDC growth charts and the derivation described above). Using the same equation above, X in the equation is the collected height and L , M , and S parameters are selected from the CDC height-for-age chart. The STAGE file contains these parameters by sex and age; it is available at the website http://www.cdc.gov/growthcharts/percentile_data_files.htm.

NOTE: The CDC growth charts are designed for use in pediatric populations (2 to 20 years of age).

Absolute change from baseline in TSQM domains

TSQM is a widely used generic measure of satisfaction with medication. It was developed from a published literature review of treatment satisfaction and qualitative research with patients with chronic illnesses. It was originally validated in a sample of patients with a variety of chronic conditions, but has been demonstrated to be a valid and reliable measure of treatment satisfaction in patients with CF. It consists of 14 items to form 4 domains: effectiveness (items 1, 2, 3), side effects (items 4, 5, 6, 7, 8), convenience (items 9, 10, 11), and global satisfaction (items 12, 13, 14).

The score of each domain is a scaled score ranges from 0 (least satisfied) to 100 (best satisfied) calculated as follows:

$$\text{Score of a domain} = 100 \times (\text{mean (non-missing scores in the domain)} - 1) / (\text{mean (the greatest possible score of the non-missing items)} - 1).$$

When the score of each domain is calculated, only one item may be missing from the domain for the domain to be considered valid.

For the side effect domain, if question 4 (As a result of taking this medication, do you experience any side effects at all?) is answered 'No', then the score of the side effect domain = 100. If question 4 is answered 'Yes', then the score of the side effect domain is calculated based on items 5, 6, 7, and 8 using the formula described above. The TSQM scoring manual is attached in Appendix G.

Pulmonary Exacerbation-related Endpoints

As specified in protocol Section 11.6.7.1, new or changed antibiotic therapy (IV, inhaled, or oral) for the following sinopulmonary signs/symptoms will be determined and documented at visits as indicated in Appendix A:

- Change in sputum
- New or increased hemoptysis
- Increased cough
- Increased dyspnea
- Malaise, fatigue, or lethargy
- Temperature above 38°C (equivalent to approximately 100.4°F)
- Anorexia or weight loss
- Sinus pain or tenderness
- Change in sinus discharge
- Change in physical examination of the chest
- Decrease in pulmonary function by 10%
- Radiographic changes indicative of pulmonary infection

For this study, pulmonary exacerbation is defined as a new or change in antibiotic therapy (IV, inhaled, or oral) for any 4 or more of the above signs/symptoms. This definition is based on the definition of a pulmonary exacerbation used in previous clinical studies, including ivacaftor clinical studies.

Pulmonary exacerbation related endpoints include:

- Number of pulmonary exacerbations
- Event of having at least 1 pulmonary exacerbation
- Time-to-first pulmonary exacerbation

Time-to-first pulmonary exacerbation is defined as days from the reference study drug initiation to the date of first pulmonary exacerbation. Subjects who do not experience any protocol-defined pulmonary exacerbation will be censored.

10.3.2.2 Analysis of Secondary Endpoints

10.3.2.2.1 Analysis of Secondary Endpoints

The analysis of secondary efficacy endpoints will be conducted for the Treatment Cohort Period 1 only.

Absolute change from baseline in LCI_{2.5}

The analysis for efficacy endpoints will be focused on within-group comparison and summaries. No between-groups comparisons will be performed.

For Treatment Cohort Period 1, the mixed model repeated measures (MMRM) analysis will be used for the Cumulative Study Period based on the FAS. It will include two treatment groups (L200/I-L/I and P-L/I) using baseline of the Previous Study Period.

The absolute change from previous study baseline (including all measurements at each visit, both on-treatment measurements and measurements after treatment discontinuation), will be included as the dependent variable; treatment group, visit, and treatment-by-visit interaction, as fixed effects; and subject as a random effect with adjustment for previous studies (Study 109 versus Study 011B), weight (<25 kg versus \geq 25 kg), and ppFEV₁ severity (<90 versus \geq 90), both as determined at screening in the previous studies, and previous study baseline LCI_{2.5} as a continuous variable.

In the model, visit will be treated as a class variable, and an unstructured covariance matrix will be assumed to model the within-subject variability. This model imposes no assumptions on the correlational structure and is considered robust. If there is a convergence problem due to the unstructured covariance matrix, the unstructured covariance matrix will be replaced by compound symmetry in the primary analysis. Denominator degrees of freedom for the *F*-test for fixed effects will be estimated using the Kenward-Roger approximation.¹ With a mixed-effects model as the primary analysis model based on restricted maximum likelihood estimation and assuming that conditional on fixed and random effects data are missing at random, no imputation of missing data will be done.

The result obtained from the model will be the treatment effect at each post baseline visit. The estimated mean within-group treatment effect, i.e., Least Square (LS) Means, SE, 95% CI, and a 2-sided within treatment group *P* value, will be provided. The LS means of absolute change from previous study baseline with 95% CI at each visit during the Cumulative Study Period will be plotted by treatment groups (L200/I-L/I and P-L/I).

Raw values and absolute change from previous study baseline, at each visit during the Cumulative Study Period, will be summarized in a separate table. Descriptive statistics, including number of subjects (*n*), mean, SD, SE, median, minimum, and maximum, will be provided.

In addition, descriptive summary statistics will be provided in a separate table for raw values and absolute change from current study baseline for P-L/I for visits in the Current Study Period using 110 FAS, including number of subjects (*n*), mean, SD, SE, median, minimum, and maximum along with the 95% CI based on Normal approximation.

Absolute change from baseline in sweat chloride

The analysis of sweat chloride will be similar to the MMRM analysis described above for LCI_{2.5}, with the absolute change from previous study baseline in sweat chloride at each visit as the dependent variable; and replacing the baseline LCI_{2.5} with baseline sweat chloride of the previous studies as a continuous covariate. Figure for sweat chloride endpoints will be plotted similar to absolute change in LCI_{2.5} above. Descriptive summary based on the current study baseline for P-L/I, similar to the summary of LCI_{2.5}, will be provided separately.

Absolute change from baseline in BMI and BMI-for-age Z-score

The analysis of BMI and BMI-for-age Z-score will be similar to the MMRM analysis described above for LCI_{2.5}, with the absolute change from previous study baseline in BMI or BMI-for-age z-score, respectively, at each visit as the dependent variable; and removing the continuous

covariate baseline LCI_{2.5}. Figure for BMI and BMI-for-age z-score will be plotted similar to absolute change in LCI_{2.5} above. Descriptive summary based on the current study baseline for P-L/I, similar to the summary of LCI_{2.5}, will be provided separately.

Absolute change from baseline in CFQ-R respiratory domain

The analysis of CFQ-R respiratory domain will be similar to those specified for the MMRM analysis of LCI_{2.5}, with the absolute change from previous study baseline in CFQ-R respiratory domain score at each visit as the dependent variable; and replacing the baseline LCI_{2.5} with baseline CFQ-R respiratory domain score of the previous studies as a continuous covariate. Figure for CFQ-R respiratory domain score will be plotted similar to absolute change in LCI_{2.5} above. Descriptive summary based on the current study baseline for P-L/I, similar to the summary of LCI_{2.5}, will be provided separately.

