12.3 Analysis Periods

Three different dosing periods will be used:

Current Dosing Period refers to the period starting with the initial dose of study drug in Study 110 to the last dose of study drug in Study 110.

Cumulative Dosing Period refers to the period starting with the initial dose of study drug in the previous study to the last dose of study drug in Study 110.

Active Dosing Period refers to the period starting with the initial dose of active treatment to the last dose of active treatment in Study 110.

Within each of the above dosing periods, safety analysis will be based on the treatment-emergent period, which starts from the start of the dosing period to 28 days (inclusive) after the last dose of the dosing period.

Handling of the data during the gap between the previous study and the rollover study will be detailed in the SAP.

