12.4 Statistical Analysis

12.4.1 General Considerations

For the Observational Cohort, summaries will only be provided for the disposition, demographic and baseline characteristics, and SAEs. Summaries will be provided based on all enrolled subjects in that cohort.

For the Treatment Cohort, analyses will be repeated for current dosing period, cumulative dosing period (efficacy only), and active dosing period as shown in Table 12-3. All analyses will be provided using all data, regardless of whether the subjects turn 12 years of age and subsequently switch to LUM 400 mg q12h/IVA 250 mg q12h, to examine the treatment strategy, which includes the age-based dose regimen switch.

Table 12-3 Analysis of Efficacy and Safety in Different Dosing Periods

Period	Efficacy	Safety
Current Dosing Period	X	X
Cumulative Dosing Period	X	None
Active Dosing Period	X	X

- Efficacy analysis (except those related to pulmonary exacerbations, LCI, [REDACTED]) will be based on the FAS for the current dosing period, and based on the IFAS for the cumulative dosing period and the active dosing period.
 - Pulmonary exacerbation-related analysis for the active dosing period will be based on 109FAS by treatment group. The placebo-controlled period for subjects randomized to the placebo arm will be analyzed separately.
 - LCI related analysis will be based on the LCI Analysis Set for the current dosing period, and based on the Integrated LCI Analysis Set for the cumulative dosing period and the active dosing period.

- Safety analysis will be based on the Safety Set for the current dosing period, and based on the Integrated Safety Set for the active dosing period.

All subject data listings for the Treatment Cohort will be referenced using the Integrated All Subjects Set, unless otherwise specified.

Continuous variables will be summarized using the following descriptive summary statistics: the number of subjects (n), mean, standard deviation (SD), median, minimum value, and maximum value.

Categorical variables will be summarized using counts and percentages.

Baseline: The baseline value of each dosing period is defined as the most recent measurement before intake of the first dose of the corresponding dosing period, except if specified otherwise.

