12.4.3 Efficacy Analysis

Assessment of the efficacy and durability of long-term treatment with lumacaftor in combination with ivacaftor in the Treatment Cohort is a secondary objective of this study.

For continuous efficacy variables: Lung clearance index ($LCI_{2.5}$ and $LCI_{5.0}$) (for subjects rolled over from Study 109 and the Study 011B LCI Substudy), sweat chloride, $ppFEV_1$ (both absolute change and relative change), BMI and BMI-for-age z-score, weight and weight-for-age z-score, height and height-for-age z-score, CFQ-R respiratory domain, and

TSQM, raw values and absolute change (or relative change) from baseline, at each visit, will be summarized. Descriptive statistics including number of subjects (n), mean, SD, standard error (SE), median, minimum, and maximum will be provided. In addition, 95% CI of the mean will be presented.

For the analyses of LCI and ppFEV₁, a mixed-effect repeated-measure model (MMRM) will be fitted for the cumulative dosing period, including visits from the previous Study 109 and Study 011B and visits from the current Study 110 based on IFAS. In the MMRM models for the cumulative dosing period, the absolute change from baseline of the previous study (including all predose measurements at each visit in the cumulative dosing period, both on-treatment measurements and measurements after treatment discontinuation), will be included as the dependent variable; treatment group, visit, and treatment-by-visit interaction as fixed effects; and subject as a random effect with adjustment for previous study (Study 109 versus Study 011B), weight (<25 kg versus ≥25 kg), and ppFEV₁ severity (<90 versus ≥90), both as determined at screening in the previous study. In the analysis of LCI, baseline LCI value will also be included as a continuous covariate in the MMRM model. The result obtained from the model will be the treatment effect at each postbaseline visit. The estimated mean treatment effect, a 95% CI, and a 2-sided *P* value will be provided. The least squares (LS) means (95% CI) at each visit will be plotted by treatment group.

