9 ANALYSIS PERIODS

9.1 Treatment Cohort Period 1

Three different Study Periods, as detailed below, will be defined and analyzed for Treatment Cohort Period 1 subjects. The safety analysis for the corresponding Study Period will be based on its treatment-emergent period.

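### The SAP calls within-group change from the parent-study baseline a treatment effect, placebo weeks included, and specifies no concurrent contrast of the Study 109 arms

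*SAP*

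**What the plan says.** SAP 10.3.2.2.1 describes an MMRM for LCI2.5 over the Cumulative Study Period on the FAS, with group, visit and their interaction. The same approach is carried to the other continuous endpoints there and in 10.3.2.2.2. The output is "The estimated mean within-group treatment effect, i.e., Least Square (LS) Means, SE, 95% CI", together with a two-sided P value within each group. The section also says: "The analysis for efficacy endpoints will be focused on within-group comparison and summaries. No between-groups comparisons will be performed". Table 10-2 (SAP 10.1.1) gives both groups rows from Study 109/011B Day 15 to Week 24 and onward into Study 110.

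Protocol 12.4.3 plans an MMRM for LCI and ppFEV1 only. Its dependent variable is "the absolute change from baseline of the previous study (including all predose measurements at each visit in the cumulative dosing period", and "The result obtained from the model will be the treatment effect at each postbaseline visit", with a 95% CI and a P value. It does not say whether that effect is a difference between groups or a change within one.

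On periods, protocol 12.4.1 says that "analyses will be repeated for current dosing period, cumulative dosing period (efficacy only), and active dosing period as shown in Table 12-3", with efficacy in general "based on the IFAS for the cumulative dosing period and the active dosing period". Protocol 12.3 defines the third of these: "Active Dosing Period refers to the period starting with the initial dose of active treatment to the last dose of active treatment in Study 110". SAP 9.1 says "Three different Study Periods, as detailed below, will be defined and analyzed for Treatment Cohort Period 1 subjects". Those three are Previous, Current and Cumulative. The Active Dosing Period is not among them.

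**The concern.** A P value for the mean change within one group tests whether anything moved since baseline. Practice effects, regression to the mean, open-label reporting and growth all count toward it. Calling the result a treatment effect invites the reader to credit the drug with all of that. In the P-L/I rows for Study 109 there was no drug to credit.

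Long-term efficacy and durability is a secondary objective (SAP 5.2), and the integrated data hold both randomised arms of Study 109 through Week 96 of Study 110. A table that tests each arm against zero and never sets one against the other leaves out the comparison that best separates drug effect from time.

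**Working it through.** **What each row of Table 10-2 estimates**

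| Group and rows | Treatment since the parent baseline | LS mean change estimates |
|---|---|---|
| L200/I-L/I, all visits | LUM/IVA (Study 011B children with a planned 2-week washout) | Change over time on LUM/IVA |
| P-L/I, Study 109 visits | Placebo | Change on placebo |
| P-L/I, Study 110 visits | 24 weeks of placebo, then LUM/IVA | A mixture of the two |

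All three carry the same label and a P value. Weight, height and BMI are modelled on the raw scale as well as by z-score. Protocol 8.2.3 itself says that weight and height rise with ordinary growth and need adjusting for age and sex. On the raw scale a nonzero change is expected in either arm without any drug effect.

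**Is the randomised comparison specified elsewhere in the SAP?** (10.3.2.2.1 and 10.3.2.2.2)

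- Exacerbation count model: it has a treatment term, but sets L200/I-L/I over the Cumulative Study Period against P-L/I over the Current Study Period. The calendar windows differ.
- Kaplan-Meier approach 1 and the at-least-one-event summary: the same two windows.
- Rate-of-change model: Placebo against L/I Overall. L/I Overall contains the same placebo children later, plus Study 011B children. The SAP does not say that a contrast is reported.
- P-L/I change from the Study 110 baseline: descriptive, with 95% CI, one group only.

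None of these is a concurrent contrast of the randomised arms.

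**The plan's own figure.** The only design figure is the table of CIs for CF lung incidence (protocol Table 12-1). It is reproduced by p ± 1.96 × √(p(1 − p)/256); for p = 0.1, 1.96 × √(0.09/256) = 0.037, giving (0.063, 0.137). All four rows match. It does not bear on this point, so the sizes below are illustrations.

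**How often placebo drift alone gives P < 0.05.** Inputs: about 200 children from Study 109 (protocol 12.1). The allocation ratio is not given, so placebo n = 67 to 100 is assumed. Drift d is in units of the SD of change, with no drug effect. The normal approximation is Φ(d√n − 1.96) + Φ(−d√n − 1.96). For d = 0.2 and n = 100, d√n = 2.0, and Φ(0.04) plus a negligible second term gives 0.52.

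| Drift d | n = 67 | n = 100 |
|---|---|---|
| 0 | 0.05 | 0.05 |
| 0.1 | 0.13 | 0.17 |
| 0.2 | 0.37 | 0.52 |
| 0.3 | 0.69 | 0.85 |
| 0.5 | 0.98 | >0.99 |

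A between-arm test with equal drift in both arms rejects 5% of the time throughout.

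**What an arm difference would deliver.** In SD units its SE is √(1/100 + 1/100) = 0.141 at 100:100 and √(1/67 + 1/133) = 0.150 at 67:133. A true difference of 0.4 SD would be detected with power 0.81 and 0.76 respectively. For LCI2.5, with 100 per arm and an assumed SD of change of 1.0 to 2.0, the 95% half-width is 1.96 × SD × √(2/100) = 0.28 to 0.55. Non-rollover and dropout would widen it.

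**Why the stated model is not enough as it stands.** L200/I-L/I combines randomised Study 109 children with non-randomised Study 011B children, and previous study enters only as a main effect. Its group difference at a given visit is therefore not a purely randomised contrast. P-L/I contains no Study 011B children, so its LS mean also depends on how the previous-study factor is weighted, which the SAP does not state. A fit on the 109 FAS (SAP 8.1) removes both problems.

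**The case against.** The strongest reply is that this is an open-label safety rollover, that Study 109 exists to compare the arms over 24 weeks (protocol 8.2.1), and that SAP 10.3.2.3 declares every efficacy P value nominal. Declining to repeat the comparison is then a defensible choice. That stands as a limit on severity. It does not justify the label on the placebo rows, and Study 109 cannot speak to early versus delayed start after Week 24.

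The reply is also right against several stronger readings that a reader might infer:

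- *That the SAP changed the baseline.* The protocol MMRM already used the parent-study baseline over the cumulative period, placebo weeks included.
- *That the SAP deleted a promised active-minus-placebo comparison.* Protocol 12.4.3 never writes one. Protocol 12.4.4 bars between-treatment testing for safety and no such bar appears for efficacy, but that is suggestive only.
- *That an active-dosing MMRM was dropped.* None was planned. By-visit efficacy for that period was descriptive with 95% CIs.
- *That active-dosing efficacy has vanished.* For L200/I-L/I the first study dose is the first active dose, so the parent baseline already serves. P-L/I has its separate table from the Study 110 baseline, and the exacerbation and slope analyses use on-drug time. What is lost is the named period and one presentation of both groups from first LUM/IVA dose.
- *That the arms are never compared anywhere.* Study 109 compares them. The gap is in the specified Study 110 outputs.

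Finally, the contrast after Week 24 is open-label, and children who stopped treatment prematurely in the parent study cannot enter the Treatment Cohort, so it leans on missing-at-random. That is fair and belongs in the table footnote.

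**Conclusion.** The point holds in this form: the SAP gives a within-group change the name and P value of a treatment effect, including where the treatment was placebo, and specifies no concurrent contrast of the randomised arms. It narrows ambiguous protocol wording. It should be corrected, but it is not critical, because efficacy is secondary, the P values are nominal and the primary safety analysis is unaffected.

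The mislabelling rests on the text alone. The sizes rest on assumptions: placebo n of 67 to 100, drift of 0 to 0.5 SD, and for the LCI2.5 half-width an SD of 1.0 to 2.0 with 100 per arm and no dropout. No precision gain from pooling all on-drug children is claimed for LCI2.5: SAP 8.3 limits the LCI Set to Study 109 and the Study 011B LCI Substudy, whose size is not given. SAP section 3 is not in the public text, so whether the sponsor explains the choice there cannot be judged.

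**What to change.** 1. In SAP 10.3.2.2.1, and wherever that model is reused, call the within-group LS means *change from baseline*. Label the P-L/I rows for Study 109 *change on placebo*. Remove treatment-effect wording from both.
2. Fit the MMRM on the 109 FAS without the previous-study term, and report L200/I-L/I minus P-L/I with 95% CI at each visit. Label it *LUM/IVA versus placebo* at Study 109 visits and *early versus delayed start* at Study 110 visits. Amend the bar on between-group comparisons to match. Keep the result nominal, and footnote the open-label phase and the missing-at-random assumption for children who did not roll over.
3. Optionally, restore the protocol's descriptive by-visit summary for the Active Dosing Period, with both groups timed from first LUM/IVA dose in one table. An MMRM for that period would be a new analysis and should be described as such.

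The cost is SAP wording, one additional model fit per continuous endpoint with its contrasts, and at most one more set of descriptive tables. No new data are needed.
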